5.3 LIFESTYLE CONSIDERATIONS

During this study, participants may maintain their current diet and level of physical activity to which they are accustomed, i.e., they will not be asked to abstain from small amounts of soy in their diet. (At time of phone screening, individuals who reported current high-dose soy consumption, use of herbal supplements, or soy or vegetarian nutrition, or any other extreme dietary habits would have been excluded from participation.)

5.4 SCREEN FAILURES

Screen failures are defined as participants who consent to participate in the clinical trial but are not subsequently randomly assigned to the study intervention or entered in the study. A minimal set of screen failure information is required to ensure transparent reporting of screen failure participants, to meet the Consolidated Standards of Reporting Trials (CONSORT) publishing requirements and to respond to queries from regulatory authorities. Minimal information includes demography, screen failure details, eligibility criteria, and any serious adverse event (SAE).

Individuals who do not meet the criteria for participation in this trial (screen failure) because of indecision about surgical treatment or temporary use of NSAIDS may be rescreened. Rescreened participants should be assigned the same participant number as for the initial screening.

5.5 STRATEGIES FOR RECRUITMENT AND RETENTION

Recruitment for this multi-site trial will take place in southern and southeastern Connecticut in the catchment areas of Yale University and Lawrence+Memorial Hospital (LMH), respectively, and in southern Rhode Island, South County Hospital's service area. Primarily, Principal Investigator [name] and Site Principal Investigator [name] II will be drawing from their and fellow Yale School of Medicine urologic oncologist's patient base meeting study eligibility criteria. Eligible patients of all ethnicities and races will be recruited without preference.

Positive post-biopsy prostate cancer patients of Drs. [name] and [name] and the urologist Co-Investigators will be identified to the Clinical Trials Manger, who will invite patients awaiting prostatectomy to meet in person for clinical screening in Yale Center for Clinical Investigation's Church Street Research Unit (CSRU), or in LMH's or SCH's urology clinic (as determined by referring physician's location). The Clinical Trials Manger will thoroughly telephone screen interested persons to ensure eligibility (i.e., they meet no exclusion criteria) before inviting and scheduling them for a face-to-face informed consent and clinical screening at the CSRU or LMH, or SCH.

If needed, the investigators may employ the services of the Yale Center for Clinical Investigation/Clinical and Translational Science Award (CTSA) for recruitment, including dedicated recruitment staff, community outreach personnel, as well as the use of the www.yalestudies.org website with targeted recruitment information.

The targeted enrollment (n=72) over the 3-year recruitment period will be met with an estimated accrual rate of 24 participants enrolled per year.

As a thank you for their time, participants will be remunerated a total of \$300 using the Bank of America reloadable card ePayment system through OnCore®, for consuming the study drink, providing blood samples, answering the questionnaire, and being available for phone check-in on a weekly basis. \$100 will be given at Visit 1 and \$200 will be given at Visit 2.

6 STUDY INTERVENTION

6.1 STUDY INTERVENTION(S) ADMINISTRATION

6.1.1 STUDY INTERVENTION DESCRIPTION

The investigational product is Q-CAN® Plus (“QC”), a fermented soybean-derived phytochemical food supplement in liquid form. QC is a commercially available GRAS beverage; the active ingredient is soybean (22%). The product’s primary constituents are the isoflavones genistin and daidzin (and respective metabolites genistein and daidzein). This trial will assess the efficacy of QC fermented soy in freeze-dried powdered form vs. placebo, in 72 adults with prostate cancer during the interim between biopsy and prostatectomy (4-10 weeks). The placebo is a brown rice-based powder matching in color and consistency with the (active) soy intervention, and is flavored with the same natural chocolate flavor and sweetener, *Siraitia grosvenorii* (monk fruit) as the soy intervention powder.

6.1.2 DOSING AND ADMINISTRATION

At Visit 1, participants will be given their allotment of assigned study drink. One week of study drink equals 14 single dose packets. (Dose escalation or dose-ranging is not applicable to this trial.) Each participant will be dispensed 10 weeks’ worth of IP (referred to as a “kit”), a box containing 140 foil pouch packets.

Participants randomized to the Intervention arm will orally consume two 12.5 g packets/day (~1 ounce/day) of the fermented soy powder, reconstituted with 8 oz. of water or juice (per packet), taken between the time of enrollment and their final study visit (Visit 2), approximately 24-48 hours prior to prostatectomy. Participants randomized to the Control arm will orally consume a matched daily dose of the placebo, reconstituted with 8 oz. of water or juice (per packet), taken between the time of enrollment and their final study visit (Visit 2), approximately 24-48 hours prior to prostatectomy.

Participants will be instructed they may drink each daily portion all at once or throughout the day, as preferred. However, once the study drink has been prepared with liquid, any portion remaining requires refrigeration until consumed. Ideally, the study drink is to be taken with food.

Participants will keep a daily account (“Daily Log for IP Intake”) of when they consumed (or did not consume) their assigned study drink. If they miss a dose, they will be instructed to record “0” on their daily log for any dose missed, and resume the following day with dosing as usual (i.e., they will not be instructed to “make up” the dose by consuming extra packets).

6.2 PREPARATION/HANDLING/STORAGE/ACCOUNTABILITY

6.2.1 ACQUISITION AND ACCOUNTABILITY

Kits of packets containing the study intervention and control will be shipped from the manufacturer directly to the YNHH pharmacy and the SCH pharmacy. Once the OnCore® statistician has informed the pharmacy of the participant’s randomization event and surgery date for prostatectomy, a member of the pharmacy team will generate the “prescription order”. The applicable pharmacy will dispense the appropriate kit to the clinical trials manager, who will then meet with the participant during Visit 1 to dispense it. Participants will be instructed to return all packets for reconciliation count/compliance at Visit 2 (whether used or unused). The clinical trials manager or designee will deliver the packets to the applicable pharmacy for final documentation and final disposition/destruction.

6.2.2 FORMULATION, APPEARANCE, PACKAGING, AND LABELING

The intervention product is Q-CAN® Plus, a fermented soybean-derived phytochemical liquid food supplement in a freeze-dried version. Q-CAN® is a commercially available GRAS beverage that has been marketed in China since 1985 and in the United States since 1991. In the US, it is marketed as a food, under Fujian Yang Zhenhua 851 Bio-Science Co., Ltd., registration number 17334630796. The active ingredient is soybean (22%), and primary constituents of the formulation are isoflavones genistin, daidzin genistein, and daidzein. The freeze-dried powder consists of fermented soy (78.2%), soy extract (1.8%), natural chocolate flavor (18%), and *Siraitia grosvenorii* (2%).

The placebo product for this trial will be a brown rice flour-based powder, matching in color and consistency with the intervention product. The placebo will contain the same flavoring (natural chocolate flavor, 18%) and sweetener (*Siraitia grosvenorii*, 2%) as the intervention, for dual purposes of matching taste (to the greatest degree possible) and masking the difference in flavor between fermented soy and brown rice powders.

Fujian Yang Zhenhua 851 Bio-Science Co., Ltd./BESO Biological Research Center, Inc., will manufacture the intervention and placebo products. The immediate packaging for both will be a sealed foil pouch, as shown below:

Nutrition and Prostate Cancer Yale IRB/HIC #2000020868
Q-CAN Plus Fermented Soy or Placebo Net weight: 12.5 g per packet
Directions for Use: Dissolve powdered contents with about 8 oz. of water; stir until dissolved, then consume.
Once powder has been added to liquid, either consume or store in refrigerator.
Caution: New Drug – Limited by Federal (or United States) law to investigational use.
Storage Conditions: Store unopened packets in cool, dry location. Once powder has been added to liquid, either consume or store in refrigerator.
Contact: [name] (Principal Investigator) at [contact] or [name] (Clinical Trials Manager) at [contact]
Lot #:
Expiration date:
BESO Biological Research Center, Inc. Diamond Bar, CA

6.2.3 PRODUCT STORAGE AND STABILITY

From an environmental standpoint, using an intervention product and placebo in powdered form imposes minimum storage requirements. To prevent moisture and contaminants from degrading the products, seal integrity of the foil packaging (primary container) for both products will be assessed at stability testing. Cardboard packaging (secondary container) will enclose both products.

The foil packets containing the intervention product and placebo product will be stored in a dedicated space at the YNHH pharmacy and at the SCH pharmacy in a temperature- and humidity-controlled room. For participants being seen in LMH, the YNHH pharmacy will currier the kits of IP to LMH pharmacy the day of or the day prior the scheduled IP dispensing visit.

6.2.4 PREPARATION

Participants will be instructed to reconstitute contents of 2 packets per day by pouring the powder into 8 oz. of water or juice (per packet) and mixing well before drinking. Also refer to section 6.1.2, Dosing and Administration.

6.3 MEASURES TO MINIMIZE BIAS: RANDOMIZATION AND BLINDING

Description of randomization and blinding procedures: A single randomization scheme for the study will be generated. This scheme will be written and validated by a system programmer in the Medical Informatics Group, Yale Center for Clinical Investigation (YCCI)/NIH CTSA, and will be incorporated into Yale's Clinical Trial Management System, OnCore®. Participants will be randomized to one of two arms, intervention or placebo control (n = 72; allocated in a 1:1 ratio to 36 per arm). Allocation will be concealed through restrictions within the OnCore® system, where neither the block nor block size can be revealed to study personnel. The randomization scheme is stratified by risk level (0-4 = low/intermediate risk, 5-10 = high risk), which is based on the Cancer of the Prostate Risk Assessment (CAPRA) score. Once made, the assignment is final and the participant will be analyzed in that group regardless of future events or information, in accordance with the intent-to-treat principle.

Plans for the maintenance of trial randomization codes and appropriate blinding: After review of eligibility criteria, the blinded clinical trials manager will access the OnCore® system to enter the participant's screening/baseline data and indicate study eligibility status, thus initiating randomization. Once a participant's study status is updated to "Eligible", this indication will then be retrieved by a blinded, specified OnCore® statistician who will perform the randomization assignment through OnCore®. The statistician will also serve as liaison to the dispensing pharmacy by sending confirmation via email to either the Yale-New Haven Hospital pharmacists or the South County Hospital pharmacist, informing them of the randomization event, in order for them to release the order for preparing the assigned IP for dispensing. The statistician will also inform the clinical trials manager when a participant has been randomized, giving an indication when the IP may be obtained from the pharmacy. The YNHH and SCH pharmacists will be necessarily unblinded to participant's randomization status. LMH pharmacists, however, will remain blinded; YNHH pharmacy will simply currier the kits needed for subject visits at LMH.

Circumstances in which the blind would be broken for an individual would be in the event of an SAE. Unblinding of all participants would occur only by the PI, with concern for a suspected or substantiated SAE associated with the intervention or placebo.

Problems anticipated: Compared to brown rice, the odor of fermented soy is distinctive and strong. The potential for unblinding of study personnel would exist in handling participants' used/opened pouches. For this reason, participants will be asked to return their packets for accountability and reconciliation in a large, re-sealable plastic bag, which will be supplied for each kit.

Intervention and control/placebo are as indistinguishable as possible: Foil pouch labeling for intervention and placebo will be identical, with the exception of lot number. The manufacturer will communicate directly with the pharmacy to ensure the dispensing pharmacists can distinguish between active and control packets.

Measures to prevent unblinding by laboratory measurements: Unblinding by laboratory measurements is highly improbable as participants with CAPRA scores at low- and high-risk levels (stratification scheme) will be randomized into each of the study's two arms.

Plans for managing and reporting inadvertent unblinding: All inadvertent unblinding will be reported to the PI. Unblinded patients would be censored from analysis and excluded from participation.

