4 STUDY DESIGN

4.1 OVERALL DESIGN

We hypothesize that QC fermented soy is beneficial in adults with prostate cancer on the basis of prior anti-cancer activity in human prostate cancer cell lines.

This is a parallel group, double-blind, randomized, phase III clinical trial. The primary aim is to assess the efficacy of Q-CAN (QC) fermented soy vs. placebo in 72 adults with prostate cancer. Subjects will be randomized to one of two arms (n=72; 36 per arm), and stratified (low/high) based on Cancer of the Prostate Risk Assessment¹¹ (CAPRA) score: 0-4=low/intermediate risk, 5-10=high risk). The two arms are:

1. **Intervention:** Daily QC (two 12.5g packets/day) (~1 ounce/day) taken between the time of enrollment and radical prostatectomy.
2. **Control:** Daily (matched dose) placebo, taken between the time of enrollment and radical prostatectomy.

This is a multi-site trial. Clinical assessments (3 study visits) will take place either in the Yale Center for Clinical Investigation's Research Outpatient Unit, or in LMH's urology clinic space, or South County Hospital (SCH) urology clinic space (as determined by the referring physician's location), at: 1) screening/baseline, 2) enrollment (~1-3 days after BL), and 3) just prior to prostatectomy, *estimated* at between 4 and 10 weeks from baseline/enrollment (see section 1.3 SOA). Length of time in the study will vary for each subject, depending on how far out their prostatectomy will occur; all prostatectomies will be scheduled to occur between 4-10 weeks post-baseline.

To minimize bias, the Medical Informatics Group will handle randomization through Yale's Clinical Trial Management System, OnCore® (Forte Research Systems, Inc., Madison, WI). The blinded study coordinator will access the OnCore® system to indicate eligibility status based on inclusion/exclusion criteria. The assignment will then be retrieved by a blinded OnCore® Statistician, who will perform randomization. Once the participant has been successfully randomized to a treatment arm, the statistician will send confirmation to the pharmacy for dispensing, and also inform the study coordinator. Once made, the assignment is final and the participant will be analyzed in that group regardless of future events or information, in accordance with the intent-to-treat principle.

For interim analysis details, refer to Section 9.4.6, Planned Interim Analysis.

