9.3 POPULATIONS FOR ANALYSES

Intention-to-treat ('as randomized') analyses will be performed on all randomized participants. Duration of treatment will be taken into account in the analysis.

Per-protocol ('as-treated') analysis will also be carried out; assessment of treatment adherence will be based on self-reported reporting during phone follow-up calls.

The Safety Analysis dataset will include participants who took at least one dose of study medication.

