9.4.8 TABULATION OF INDIVIDUAL PARTICIPANT DATA

For analytical purposes, participants will be counted in the group to which they were randomized, i.e. intent-to-treat analysis.

Individual participant level data will be presented only in the case of safety data monitoring and as requested by the DSMC and/or IRB.

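### Section 6.3 drops unblinded men from the analysis, contradicting the protocol's rule that all randomized men are analyzed as assigned

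*Protocol*

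**What the plan says.** The exclusion is the last sentence of Protocol section 6.3, in the paragraph on inadvertent unblinding: "Unblinded patients would be censored from analysis and excluded from participation".

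Four other places set the analysis rule:

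- Section 6.3, on randomization: "Once made, the assignment is final and the participant will be analyzed in that group regardless of future events or information".
- Section 4.1: "the participant will be analyzed in that group regardless of future events or information, in accordance with the intent-to-treat principle".
- Section 9.3: intention-to-treat "analyses will be performed on all randomized participants".
- Section 9.4.8: "participants will be counted in the group to which they were randomized".

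Section 9.3 also plans a per-protocol analysis, for which "assessment of treatment adherence will be based on self-reported reporting during phone follow-up calls". Blinding status plays no part in it.

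Section 6.3 describes two routes to unblinding. One is deliberate: "Circumstances in which the blind would be broken for an individual would be in the event of an SAE". The other is smell: "Compared to brown rice, the odor of fermented soy is distinctive and strong". The protocol raises the smell as a risk to study staff who handle opened pouches.

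The SAP repeats the primary analysis text but defines no analysis population and does not mention unblinding.

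**The concern.** An intention-to-treat set should not depend on something that happens after randomization. Here the triggering event may also be related to arm, because the smell that could reveal the assignment belongs to the active product. If removed men also differ from the rest in PSA change, the arm comparison is biased.

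The rule is also hard to apply. The protocol does not say whether a man counts as unblinded when only a staff member has guessed his arm, or whether a code break for a serious adverse event counts. If it does, men would leave the primary analysis because of a safety event.

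The exclusion gains little. PSA is measured in one central laboratory (section 8.1), so knowledge of the arm has little room to affect the value. Used and unused packets come back at Visit 2 (section 6.2.1), the visit at which the final blood sample is taken (section 8.1). By the pouch route, then, the rule would mostly discard a man whose final PSA is being collected anyway.

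**Working it through.** **Text check.** The contradiction needs no arithmetic.

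1. Unblinding can occur only after assignment, so it is a later event of the kind sections 4.1 and 6.3 say must not affect how a man is analyzed.
2. Section 9.3 includes all randomized men. A man censored under 6.3 is randomized but not analyzed.
3. The exclusion could be harmless if it applied only to the per-protocol set. Section 9.3 ties that set to self-reported adherence, and 6.3 does not name a set.
4. The SAP does not settle the matter.

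**The plan's own figure (background).** Section 9.2 gives a difference of 15 units, SD 20.3, 80% power and two-sided 0.05. The normal formula is n per arm = 2 × (1.960 + 0.842)² × 20.3² / 15² = 28.8, so 29 per arm and 58 in all. The t-based version gives 30 per arm and 60 in all. Neither is the planned 72, and no inflation is stated. This gap does not affect the present point. At 36 per arm, t-based power is 87.1%.

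**Possible size.** The documents give no unblinding count, so k and d below are assumptions. Let k of n = 36 men be removed from one arm, and let d be their mean PSA change minus that of the retained men. The arm mean then shifts by (k/n) × d:

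- k = 2, d = 10: 2/36 × 10 = 0.56 units (3.7% of 15)
- k = 2, d = 20.3: 2/36 × 20.3 = 1.13 units (7.5%)
- k = 4, d = 10: 4/36 × 10 = 1.11 units (7.4%)
- k = 4, d = 20.3: 4/36 × 20.3 = 2.26 units (15.0%)

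The consequences for a pooled two-sample t-test come from the noncentral t distribution with arms of 36 − k and 36. The SD of change is taken as 20.3, although section 9.2 does not say that its SD refers to change. The noncentrality is the shift (for type I error) or 15 (for power), divided by 20.3 × √(1/(36 − k) + 1/36).

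| k removed from one arm | Type I error, d = 0 | d = 10 | d = 20.3 | Power at 15 units, d = 0 |
|---|---|---|---|---|
| 0 | 5.0% | – | – | 87.1% |
| 2 | 5.0% | 5.15% | 5.60% | 86.1% |
| 4 | 5.0% | 5.57% | 7.36% | 85.0% |

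**The case against.** The best counter-argument is that the sentence is operational text that no analyst would follow. It appears once, in a paragraph on handling accidental unblinding, and neither section 9 nor the SAP repeats it. That makes its use less likely. But no clause says which section prevails, and the sentence is explicit about analysis.

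*Censored* could mean only that data after unblinding are not used. Section 9.4.2 allows a linear mixed model, which can retain a man with a baseline PSA alone. Removal is the more natural reading. Even on the milder one, a PSA collected after unblinding would be dropped because of a post-randomization event, so the conflict remains.

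Some narrower objections stand:

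- Section 9.4.8 is weaker support than 4.1, 6.3 and 9.3. It concerns the arm in which a man is counted and does not by itself forbid exclusions.
- Read in place, the sentence most naturally covers accidental unblinding. Its extension to code breaks is a possible reading, not a clear one.
- The numerical range is assumption on assumption. No document links unblinding to PSA change, and for the pouch route such a link is doubtful. A d of 20.3 is 20.3/15 = 1.35 times the whole design effect. SAP section 1 also says full enrollment was not reached, so 36 is not the achieved arm size. Smaller arms would make k/n larger for the same k.

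**Conclusion.** The concern holds. Section 6.3 imposes a post-randomization exclusion that sections 4.1, 6.3 and 9.3 rule out, so the primary analysis set is stated in two incompatible ways. That conclusion rests on the text alone and is firm.

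Bias is possible but not demonstrated, and its size and direction cannot be derived. Under the stated assumptions the shift is 0.6 to 2.3 units and type I error 5.1% to 7.4%. If removed men resemble the rest, the cost is one to two percentage points of power. The effect is likely small. The documents do not report that any man was unblinded or removed, so the sentence may have affected no one. It should still be corrected, because it concerns the primary analysis and the repair is cheap.

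**What to change.** Replace the sentence in section 6.3 with wording such as:

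> Men who are unblinded, whether inadvertently or by a code break for a serious adverse event, remain in the intention-to-treat analysis in their assigned arm, using any PSA collected. They may be excluded only in a sensitivity or per-protocol analysis.

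In addition:

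- Define whether unblinding of staff alone counts, and report unblindings by arm, route and timing relative to the final PSA.
- In section 9.3 and the SAP, state that the intention-to-treat set includes unblinded, discontinued and replaced men. For replaced men this only confirms section 9.3.
- As a side clarification, reconcile the two statements in section 7.1: one seeks remaining data after a man stops product, the other gathers no new health information after withdrawal or discontinuation. The text should separate stopping product from withdrawing consent for data, because a man excluded before Visit 2 may otherwise have no final PSA.

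Whether an unblinded man continues in the study or on product is for the sponsor to reconcile; no rule is proposed here.

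The cost is wording only, with no new visits or data. Keeping men who are off product may slightly dilute the estimate, and the number randomized may exceed the number of completers. SAP section 1 describes the analyses in the past tense, so any change made after the data were analyzed should be labelled post hoc.
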